6.3. Missing Data

Partial dates of medications will be imputed solely for the purpose of defining prior/concomitant status for medications. Dates will be defined using the hierarchy of derivations below.

- For missing start day where month and year are present, the start day will be set to the 1st of the month, unless the month and year are the same as the first dose month and year and the 1st of the month is before the first dose date, in which case, the start date will be set to the first dose date.
- For missing start day and month where year is present, the start day and month will be set to January 1st, unless the year is the same as the first dose year and January 1st is before the first dose date, in which case, the start date will be set to the first dose date.
- For missing end day where month and year are present, the end day will be set to the last day of the month, unless the month and year are the same as the trial termination month and year, in which case, the end date will be set to the trial termination date.
- For missing end day and month, where year is present, the end date will be set to the trial termination date if the years are the same. If the trial termination year is greater than the end year, the end day and month will be set to December 31st.

Partial onset dates for adverse events will be imputed in the same manner described above for partial start dates for the purpose of defining treatment emergent status.

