- Intrauterine hormone-releasing system (IUS)
- Bilateral tubal occlusion
- Vasectomized male partner
 - Vasectomized partner is a highly effective birth control method provided that
 partner is the sole sexual partner of the woman of childbearing potential study
 participant and that the vasectomized partner has received medical assessment of
 the surgical success.
- Sexual abstinence (defined as refraining from heterosexual intercourse during the entire period of exposure associated with the study treatment).
 - In the context of this guidance, sexual abstinence is considered a highly effective method only if defined as refraining from heterosexual intercourse during the entire period of risk associated with the study treatments. The reliability of sexual abstinence needs to be evaluated in relation to the duration of the clinical study and the preferred and usual lifestyle of the subject.

Adapted from: Clinical Trials Facilitation Group (CTFG). Recommendations Related to Contraception and Pregnancy Testing in Clinical Trials. September 15, 2014.

Available at: https://www.hma.eu/fileadmin/dateien/Human_Medicines/01-About_HMA/Working_Groups/CTFG/2014_09_HMA_CTFG_Contraception.pdf

PROHIBITED MEDICATIONS LIST

Examples below are not exclusive.

- Any new stimulant for the treatment of ADHD that the subject was not taking at Baseline is also prohibited.
- Other medications used to treat TS are prohibited.
- Dopamine depleting medications are prohibited.
- D2 receptor antagonists are prohibited.

Prohibited Antipsychotic Medications		
Aripiprazole	Loxapine	
Cisapride	Methylphenidate	
Clonidine	Paliperidone	
Dextroamphetamine	Pimozide	
Dronedarone	Risperidone	
Droperidol	Thioridazine	
Fluoxetine	Topiramate	
Guanfacine	Ziprasidone	
Haloperidol		

Other Prohibited Medications for the Treatment of Tics	Mechanism
Any dopamine agonist (e.g., ropinire	ole, pramipexole)
Baclofen	GABA-B receptor agonist
Clonazepam	GABA-A receptor positive allosteric modulation
Duetetrabenazine	VMAT2 inhibitor / monoamine depleter
Guanfacine	Alpha-2A adrenergic receptor agonist
Reserpine	VMAT1/2 inhibitor / inhibits uptake of dopamine
Tetrabenazine	VMAT2 inhibitor / monoamine depleter
Valbenazine	VMAT2 inhibitor / monoamine depleter

Other Prohibited Medications	Mechanism
Chloroethylnorapomorphine	D2 receptor antagonist
Chlorpromazine	D2 receptor antagonist/ antipsychotic
Cinnarizine	Antihistamine/ calcium channel blocker/ Interaction with D2 receptors

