7.4.1. Prior Medication

Prior medications are defined as medications entered in the eCRF that either start, or end before the first dose of study medication. Prior medications will be summarized by ATC level 2 and preferred drug name for the Safety Set.

Prior medications which continue after first dose of study medication will also be classified as a concomitant medication.

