7.4.2. Concomitant Medication

Concomitant medications are defined as medication on the eCRF that are taken on or after or are ongoing at the start date of dosing. Concomitant medications will be summarized by ATC level 2 and preferred drug name for the Safety Set.

This document is confidential.

8. Efficacy

The mITT as well as ITT set will be used for the analysis of the efficacy endpoints.

The YGTSS, CGI-TS-S, and C&A-GTS-QOL will be assessed at Baseline, Months 1, 3, 6, 9 and 12. The CGI-TS-I will be assessed at Months 1, 3, 6, 9 and 12.

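### SAP 6.3 moves a partial medication start or AE onset to the first dose date without checking whether the stop or end date already falls before it

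*SAP*

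**What the plan says.** SAP 6.3 states why medication dates are imputed: "Partial dates of medications will be imputed solely for the purpose of defining prior/concomitant status for medications". When only the day of a start is missing, the 1st is used. The exception, for a start in the month and year of first dose, applies if "1st of the month is before the first dose date, in which case, the start date will be set to the first dose date". When only the year is known, January 1st is used, unless the year is that of first dose and "January 1st is before the first dose date, in which case, the start date will be set to the first dose date".

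End dates are filled separately and as late as possible: "For missing end day where month and year are present, the end day will be set to the last day of the month", with the trial termination date used in the termination month. A year-only end is handled likewise. No start rule refers to the end date, and no end rule refers to the start. The closing sentence of 6.3 carries the start rules over to AE onset, to decide treatment-emergent status.

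Three definitions then use these dates:

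- SAP 7.4.1: "Prior medications are defined as medications entered in the eCRF that either start, or end before the first dose of study medication". It adds: "Prior medications which continue after first dose of study medication will also be classified as a concomitant medication".
- SAP 7.4.2: "Concomitant medications are defined as medication on the eCRF that are taken on or after or are ongoing at the start date of dosing".
- SAP 6.2 makes an AE treatment-emergent if it starts or worsens on or after the first open-label dose. SAP 9.3 says much the same and closes the window 30 days after the last dose.

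SAP section 10, which lists departures from the protocol and additions made after database lock, does not touch the partial-date rule.

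**The concern.** Moving an unknown start to first dose is a reasonable convention when the record leaves open whether the drug or event began before or after Day 1. It is not reasonable when the record settles the question. A stop or end before Day 1 proves that the start was also before Day 1, yet the rule as written still places the start at first dose.

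On the medication side this yields records whose start follows their stop. Drugs given up before ecopipam may then be counted as taken with it. On the AE side the consequence is more direct. Treatment-emergent status depends on onset, SAP 9.3 focuses its summaries on TEAEs, and safety is the primary objective. Protocol 12.4 collects AEs from the signing of consent, so events that resolved before the first dose can be in the database.

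**Working it through.** The plan gives no figure to reproduce, so the check applies the rules of SAP 6.3, 7.4.1, 7.4.2 and 6.2 literally to test records.

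**Assumptions (not in the documents):** first dose 15 September 2020; trial termination 14 September 2021.

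**Two readings of concomitant.** Start-driven: the start is on or after first dose, or the drug is not known to have ended before it. Stop-aware: the drug did not end before first dose.

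| Recorded start | Recorded stop | Start under 6.3 | Stop under 6.3 | Prior | Concomitant, start-driven | Concomitant, stop-aware |
|---|---|---|---|---|---|---|
| 2020 | 31 Mar 2020 | 15 Sep 2020 | 31 Mar 2020 | yes | yes | no |
| 2020 | Mar 2020 | 15 Sep 2020 | 31 Mar 2020 | yes | yes | no |
| Sep 2020 | 10 Sep 2020 | 15 Sep 2020 | 10 Sep 2020 | yes | yes | no |
| 2020 | ongoing | 15 Sep 2020 | none | no | yes | yes |
| Sep 2020 | ongoing | 15 Sep 2020 | none | no | yes | yes |
| Aug 2020 | ongoing | 1 Aug 2020 | none | yes | yes | yes |
| 2019 | ongoing | 1 Jan 2019 | none | yes | yes | yes |

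**Reversed dates (rows 1 to 3).** From 31 March to 15 September is 30 + 31 + 30 + 31 + 31 + 15 = 168 days, so the start falls 168 days after the stop. In row 3 it falls 15 − 10 = 5 days after. The reversal occurs on either reading. Prior status survives because the end is before first dose. Whether the drug is also concomitant depends on which reading is programmed.

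**With a stop-date check.** Rows 1 and 2 take 1 January 2020 as the start and row 3 takes 1 September 2020. All three become prior only, and no date is reversed. Rows 4 to 7 do not change.

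**AE counterpart.** Give an AE the dates of row 3: onset September 2020 with no day, end 10 September 2020. Onset is set to 15 September, 5 days after the event ended. It meets the on-or-after-first-dose test of SAP 6.2 and is counted as a TEAE. With an end-date check, onset is 1 September and the event is not a TEAE. The definition turns on onset, so it contains nothing that would exclude an event already over.

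**Is the shift itself wrong when no earlier stop is known?** If true starts are spread evenly over the leap year 2020 (an assumption), the share of year-only starts that precede Day 1 is the number of days before first dose divided by 366:

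- first dose 15 January: 14/366 = 4%
- 15 June: 166/366 = 45%
- 15 September: 258/366 = 70%
- 15 December: 349/366 = 95%

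The shift is therefore mostly right early in the year and mostly wrong late in it. An earliest-date rule has the opposite pattern.

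**The case against.** **Limits that stand.** SAP 7.4.2 speaks of drugs taken or ongoing, not of start dates. A program that follows it by stop date would leave rows 1 to 3 out of the concomitant table. For AEs, shifting an unknown onset to first dose is a common conservative choice. The exposed AE window is also narrow, running from consent to first dose. Protocol 13.2.1 even describes AE documentation as beginning at first dose, in tension with Protocol 12.2.1 and 12.4; data collected that way would contain no pre-dose AEs to misclassify. These points limit the size of the problem. They do not justify overriding a known end date, and the SAP nowhere states the check that would prevent it.

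**Stronger readings that a reader might infer, and that the documents do not support:**

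- *Every shifted drug begun before Day 1 gets the wrong status.* A drug with a stop before Day 1 remains prior under SAP 7.4.1, and a stop-aware program classifies it correctly.
- *The shift should be dropped for medications altogether.* It is right for drugs truly begun on or after Day 1. Always using the earliest date would, under the even-spread assumption and a 15 January first dose, label as prior the 352/366 = 96% of year-only starts that were not. For ongoing drugs with an ambiguous start, the choice is a convention.
- *A long-standing stimulant would look like a breach of the rule that* "Any new stimulant for the treatment of ADHD that the subject was not taking at Baseline is also prohibited". A drug begun in an earlier year is never shifted. The medication tables are organised by ATC level 2 and drug name and carry no start dates. Listings show missing date parts as dashes (SAP 12.2.5.3). Nothing in the SAP uses imputed dates to identify prohibited drugs.
- *The durability results are affected.* No efficacy analysis in SAP section 8 uses medication status.

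**Conclusion.** The rule is wrong as written on one specific point: it ignores a recorded stop or end before first dose. For medications the certain result is a start after the stop. A false concomitant count follows only if the program works from the start date. For AEs, an event known to be over before Day 1 is counted as treatment-emergent under SAP 6.2.

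The effect is confined to partial dates in the first-dose month and year, or year-only dates in the first-dose year, with a stop or end before Day 1. The documents give no count of such records, so the number of misclassified drugs or events cannot be calculated; it is probably small. The outputs exposed are the medication summaries and the TEAE summaries. The day counts above rest on an assumed first dose date and illustrate the mechanism only.

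**What to change.** Amend SAP 6.3 so that a partial start or onset moves to the first dose date only when the stop or end date is missing, ongoing, or on or after first dose. Otherwise impute the earliest possible date (the 1st of the month or January 1st). Where the stop or end is itself partial, compare its latest possible date with first dose. The existing end rules already supply that date for medications; SAP 6.3 gives no end rule for AEs, so a clause is needed there. State in SAP 7.4.2 that concomitant status comes from the stop date or ongoing flag. The convention for prior status of ongoing drugs with an ambiguous start need not change.

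The cost is one or two sentences in SAP 6.3, the short clarification in 7.4.2, and a re-run of Tables 14.1.4.1 and 14.1.4.2 and the TEAE tables (14.3.1.x). No new data are needed.

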6.4. Visit Windows

The following visit windows will be used in the summarization or analysis of safety laboratory, vital signs, ECG, and physical exam data. If more than 1 data point falls within the window, then the data point

This document is confidential.

closest to the target day will be used. If there are 2 data points equidistant to the target day, one high and one low, then the high data point will be used. Visit windowing will not be applicable to follow-up visits.

If Baseline is Day 1, then:

Month 1 (target day = 29) 2 - 42

Month 2 (target day = 57) 43 - 70

Month 3 (target day = 85) 71 - 98

Month 4 (target day = 113) 99 - 126

Month 5 (target day = 141) 127 - 154

Month 6 (target day = 169) 155 - 182

Month 7 (target day = 197) 183 - 210

Month 8 (target day = 225) 211 - 238

Month 9 (target day = 253) 239 - 266

Month 10 (target day = 281) 267 - 294

Month 11 (target day = 309) 295 - 322

Month 12 (target day = 337) 323 and above (and not a follow-up visit)

For all efficacy and safety scales a modified last observation carried forward (LOCF) approach will be used to reassign Early Termination visits. Early Termination visits will be assigned to the next scheduled visit (per Schedule of Assessments for the parameter) after a subjects' latest scheduled visit before early termination.

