- 15) Subjects with a lifetime history of bipolar disorder type I or II, dementia, schizophrenia, or any other psychotic disorder.
- 16) Inability to swallow tablets.
- 17) Subjects with a known hypersensitivity to ecopipam or any of its excipients.
- 18) Any subject who in the opinion of the investigator is not a suitable candidate for the study.

Investigational product, dosage and mode of administration:

Ecopipam HCl will be supplied as 12.5-, 37.5-, 50-, 75-, and 100-mg tablets. The target dose is 2 mg/kg via oral administration.

Subjects will be dosed according to the following weight bands to better achieve the 2 mg/kg/day target dose: $\geq 18-\leq 23$ kg, $\geq 23-\leq 34$ kg, $\geq 34-\leq 44$ kg, $\geq 44-\leq 68$ kg, $\geq 68-\leq 83$ kg, ≥ 83 kg.

During the 4-week titration period, the following ecopipam HCl doses will be administered for each of the weight bands:

- Those who weigh ≥18-≤23 kg will titrate from 12.5 mg daily to 37.5 mg daily: 12.5 mg during Week 1, 25 mg during Week 2, and 37.5 mg during Weeks 3 and 4.
- Those who weigh >23-\le 34 kg will titrate from 12.5 mg daily to 50 mg daily: 12.5 mg during Week 1, 25 mg during Week 2, 37.5 mg during Week 3, and 50 mg during Week 4.
- Those who weigh >34- \leq 44 kg will titrate from 12.5 mg daily to 75 mg daily: 12.5 mg during Week 1, 25 mg during Week 2, 50 mg during Week 3, and 75 mg during Week 4.
- Those who weigh >44-≤68 will titrate from 25 mg daily to 100 mg daily: 25 mg during Week 1, 50 mg during Week 2, 75 mg during Week 3, and 100 mg during Week 4.
- Those who weigh >68- \leq 83 kg will titrate from 25 mg daily to 150 mg daily: 25 mg during Week 1, 50 mg during Week 2, 100 mg during Week 3, and 150 mg during Week 4.
- Those who weigh >83 kg will titrate from 25 mg daily to 200 mg daily: 25 mg during Week 1, 50 mg during Week 2, 100 mg during Week 3, and 200 mg during Week 4.

During the 52-week treatment phase, the following ecopipam doses will be administered for each of the weight bands:

- Those who weigh $\ge 18 \le 23$ kg will receive 37.5 mg daily.
- Those who weigh >23-\le 34 kg will receive 50 mg daily.
- Those who weigh >34-≤44 will receive 75 mg daily.
- Those who weigh >44-≤68 kg will receive 100 mg daily.
- Those who weigh >68-\le 83 kg will receive 150 mg daily.
- Those who weigh >83 kg will receive 200 mg daily.

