At the end of the 52-week treatment phase, subjects will titrate off therapy and receive ecopipam HCl doses that will be reduced by 25 mg/day until off drug.

Duration of treatment:

52-weeks, until New Drug Application (NDA) approval, or until development of the study drug is discontinued by the Sponsor, whichever is sooner.

Criteria for evaluation:

Safety: Study Visits may be completed in locations other than clinic and/or safety and efficacy assessments required at these visits will be made available for remote administration due to restrictions as a consequence of the COVID-19 pandemic or other qualifying event. Safety will be monitored throughout the study at every visit by repeated adverse event (AE) monitoring, vital signs, the Columbia-Suicide Severity Rating Scale (C-SSRS), the Abnormal Involuntary Movement Scale (AIMS), the Barnes Akathisia Rating Scale (BARS), the Pediatric Anxiety Rating Scale (PARS) and Children's Depression Rating Scale-Revised (CDRS-R). In addition to these assessments, at Baseline, Months 1, 3, 6, 9 and 12 safety will also be monitored by clinical and laboratory evaluations and electrocardiogram (ECG) monitoring. At the Follow Up visits, AE monitoring, the C-SSRS, clinical and laboratory evaluations and vital signs will be assessed. Laboratory evaluations will include hematology, chemistry, urine values and HbA1c. A Follow Up phone call will be conducted 30 days after the last dose of study medication to assess AEs. Subjects will be monitored for signs of abuse, and withdrawal or dependence.

Efficacy: The YGTSS, CGI-TS-S and C&A-GTS-QOL will be conducted at Baseline and Months 1, 3, 6, 9 and 12. The CGI-TS-I will be conducted at Months 1, 3, 6, 9, and 12.

All safety and efficacy variables will be summarized descriptively.

Additional analyses may need to be conducted for data not collected at sites and/or collected via remote administration due to restrictions as a consequence of the COVID-19 pandemic or other qualifying event, these additional analyses will be specified in the SAP.

	3	•	TABLE	OF	CON	TENTS
--	---	---	--------------	----	-----	-------

1.	PROTOCOL AMENDMENT CHANGES	2
SIGNATU	RE PAGE	10
INVESTIG	GATOR'S AGREEMENT	11
PROCEDU	JRES IN CASE OF EMERGENCY	12
2.	SYNOPSIS	13
3.	TABLE OF CONTENTS	17
4.	LIST OF ABBREVIATIONS AND DEFINITIONS OF TERMS	20
5.	INTRODUCTION	21
5.1.	Background on Tourette's Syndrome	21
5.1.1.	Disrupted Dopamine Systems in Tourette's Syndrome	22
5.2.	Background on Ecopipam.	23
Cl		

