3.8. Study Procedures and Flowchart

Subjects will complete study visits every month for 1 year. Follow Up visits will be conducted 7 and 14 days after the last dose of study medication and a Follow Up phone call will be conducted 30 days after the last dose of study medication.

See Appendix section 16.1 for the Schedule of Assessments.

This document is confidential.

4. Endpoints

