6.1. General Methods

All analyses and outputs will be produced using SAS® version 9.4 or later. Continuous variables will be summarized using the number of observations (n), mean, standard deviation (SD), median, minimum, and maximum. Categorical variables will be summarized using frequency counts (n), and percentages.

All relevant subject data will be included in listings. All subjects entered the database will be included in subject data listings. All by visit summaries will use the nominal visit. Unscheduled visits will not be summarized but will be included in the listings.

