9.4. Laboratory Evaluations

Blood samples for hematology and biochemistry are to be collected at Baseline, Months 1, 3, 6, 9 and 12 and One and Two Weeks Post Last Dose. Urine samples for urinalysis will be collected at Baseline, Months 1, 3, 6, 9 and 12. HbA1c will be measured at Months 1, 3, 6, 9 and 12. All results will be provided using International System of Units (SI).

Descriptive statistics for hematology, biochemistry, urinalysis and HbA1c will be provided for each test parameter and for change from baseline by visit. Shift tables (i.e., low-normal-high at Baseline versus low-normal-high at each post-baseline visit in a 3-by-3 contingency table) will be provided for hematology, biochemistry, urinalysis and HbA1c to assess changes from Baseline in laboratory values by visit. Shift (0.5% change ranging from $<4.0\%$ to $>7.5\%$) from baseline will be summarized for HbA1c by visit. Also shift (<170 , $170-199$, ≥ 200) from baseline for total cholesterol will be summarized by visit.

Separate listings will be provided for all laboratory evaluations (hematology, biochemistry, urinalysis and HbA1c).

This document is confidential.

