9.5. Vital Signs

Vital sign measurements including sitting systolic blood pressure, sitting diastolic blood pressure, sitting pulse rate, supine orthostatic systolic blood pressure, supine orthostatic diastolic blood pressure, supine pulse rate, standing orthostatic systolic blood pressure, standing orthostatic diastolic blood pressure, and standing pulse rate at each scheduled time and changes from baseline in vital sign measurements will be summarized with descriptive statistics at each scheduled time point.

Body height will be measured at Baseline and will be summarized. Weight will be measured at each schedule visit and, along with changes from baseline, will be summarized with descriptive statistics at each scheduled time point. Weight will be displayed in kilograms; height will be displayed in centimeters.

Body mass index (BMI) will be derived from the weight at each visit and from height (at screening), along with changes from baseline, will be summarized with descriptive statistics at each schedule timepoint.

BMI will be displayed in kilograms per meter squared.

The Centers for Disease Control and Prevention (CDC) growth charts will be used to calculate weight z-score, height z-score and BMI z-scores. Shift (0.5 change ranging from <-3 to >3) from baseline will be summarized for weight z-score, height z-score and bmi-z score by visit. Mean BMI, height and weight z-scores over time will be illustrated in a figure.

Heart rate outliers such as >25% decrease change from baseline, <50, >25% decrease change from baseline and <50 as well as >25% increase change from baseline, >100, >25% increase change from baseline and >100 will be summarized by visit and overall.

All vital signs data will be presented in a listing.

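### SAP 6.4 windows use 28-day months (Month 12 = day 337); on the stated 1-year schedule Months 7–11 are labelled one month late and Month 11 vital signs replace Month 12

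*SAP*

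**What the plan says.** SAP Section 6.4 applies study-day windows to four data types: safety laboratory, vital signs, ECG and physical examination. With Baseline as Day 1, the targets run 29, 57, 85 and so on to the last line, "Month 12 (target day = 337) 323 and above (and not a follow-up visit". If several records fall in one window, the one "closest to the target day will be used".

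Section 6.1 gives a different rule with no exception: "All by visit summaries will use the nominal visit". Section 10 lists the windowing among the updates made after database lock.

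On the schedule, SAP Section 3.8 says "Subjects will complete study visits every month for 1 year", and Protocol Section 7.1 agrees. The protocol synopsis adds a length in weeks: "During the 52-week treatment phase, the following ecopipam doses will be administered" and "At the end of the 52-week treatment phase, subjects will titrate off therapy". The schedule of assessments allows ±3 days per visit but gives no target study days.

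On frequency, SAP Section 9.5 says "Weight will be measured at each schedule visit and, along with changes from baseline", and vital signs are scheduled at every monthly visit. SAP Section 9.4 says "HbA1c will be measured at Months 1, 3, 6, 9 and 12". ECGs and physical examinations follow the same Month 1, 3, 6, 9 and 12 pattern.

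**The concern.** Twelve 28-day months make 48 weeks, not a year. If visits are a twelfth of a year apart, each falls a little over two days further behind its window target every month. By mid-study the lag reaches the window edge, and later visits take the next month's label.

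Long-term safety is the primary objective, and these are its by-visit tables. Two results would be misreported:

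- **Vital signs (monthly).** Months 11 and 12 compete for one row, so end-of-study weight, blood pressure and heart rate could drop out of the Month 12 summary. Weight-based BMI and z-scores would follow if they are built on windowed data.
- **Laboratory tests, ECG, physical examination.** Month 9 data, and many Month 6 data, would appear under months when none is scheduled. This includes the HbA1c, cholesterol and QTc shift tables.

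Sections 6.1 and 6.4 also give two programmers two different sets of tables from the same data.

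**Working it through.** **Inputs.** Targets, windows and the closest-to-target rule: SAP 6.4. Monthly visits for 1 year: SAP 3.8 and Protocol 7.1. Fifty-two weeks: protocol synopsis. Visit tolerance of ±3 days: Protocol Table 2. Assumption: the 12 visits are evenly spaced over 52 weeks counted from Baseline.

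**Step 1: reproduce the SAP grid.** Target for month k = 1 + 28k. This gives 29, 57, 85, 113, 141, 169, 197, 225, 253, 281, 309, 337. Windows of target − 14 to target + 13 reproduce Months 2–11 exactly; Month 1 is 2–42 and Month 12 is 323 onward. Since 12 × 28 = 336 days, day 337 is the end of week 48. On the stated schedule Month 12 is 1 + 364 = day 365, which is 28 days later.

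**Step 2: place the stated schedule in the grid.** Spacing is 364/12 = 30.33 days, a drift of 30.33 − 28 = 2.33 days per month. On-time day = 1 + 30.33k, rounded.

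| Visit | On-time day | Own window | Window assigned | Late days, of the 7 in ±3 |
|---|---|---|---|---|
| Month 6 | 183 | 155–182 | Month 7 | 4 |
| Month 7 | 213 | 183–210 | Month 8 | 6 |
| Month 8 | 244 | 211–238 | Month 9 | 7 |
| Month 9 | 274 | 239–266 | Month 10 | 7 |
| Month 10 | 304 | 267–294 | Month 11 | 7 |
| Month 11 | 335 | 295–322 | Month 12 | 7 |
| Month 12 | 365 | 323 onward | Month 12 | 0 |

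On-time Months 1–5 keep their own labels. The twelve visits therefore occupy eleven windows: Month 6 is left empty and Month 12 holds two visits.

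**Step 3: which record the Month 12 vital-sign row keeps.** On time, Month 11 is |335 − 337| = 2 days from target and Month 12 is |365 − 337| = 28 days. Across ±3 days, Month 11 spans days 332–338, at most 5 days from target. Month 12 spans 362–368, at least 25 days away. Month 11 is closer in all 7 × 7 = 49 combinations. Laboratory, ECG and physical-examination data have no scheduled Month 11 record, so their Month 12 value survives.

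**Step 4: sensitivity to spacing.**

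- *Calendar months*, over 1,461 consecutive start dates (a four-year cycle): on-time Months 7–11 are one window late for every start date, and Month 6 for 1,095 (75%).
- *30 days:* Month 6 (day 181) stays correct when on time. Late days are 4 of 7 for Month 7, 6 of 7 for Month 8 and 7 of 7 for Months 9–11. Distances from day 337 are 6 days (Month 11) and 24 days (Month 12), so Month 11 is still kept.
- *28 days:* nothing moves.

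**Step 5: break-even spacing.** An on-time visit leaves its window once 1 + s·k exceeds the upper limit, that is, at s = upper limit / k.

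| Visit | Upper limit / k | Break-even spacing (days) |
|---|---|---|
| Month 6 | 182/6 | 30.33 |
| Month 7 | 210/7 | 30.0 |
| Month 8 | 238/8 | 29.75 |
| Month 9 | 266/9 | 29.56 |
| Month 10 | 294/10 | 29.4 |
| Month 11 | 322/11 | 29.27 |

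**The case against.** The strongest reply is that neither document fixes visit days, so sites may have worked to 28-day months. There is some support for this. SAP Section 9.1 bands exposure in 28-day steps ending at day 336, and Section 10 lists that by-days table as another post-lock addition. Titration lasts 4 weeks, so a Month 1 visit at its end would be day 29. This stands as a limit on the consequences: actual dates are not in the documents, and the size of the effect cannot be fixed without them. It does not clear the plan. Section 9.1 also divides by 30.25 to express exposure in months, which makes day 337 only 337/30.25 = 11.1 months. If visits really were 28 days apart, Month 12 is week 48 and the 1-year/52-week description is wrong.

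Section 6.4, being specific and later, can be read as overriding 6.1. That is reasonable, but it puts the 28-day grid in force, and 6.1 still lacks the exception.

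The 52-week figure appears only in the protocol synopsis; the SAP says 1 year. It is also unstated whether the 52 weeks include titration. Both points bear on the exact replacement targets. Neither moves Month 12 back to day 337.

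Finally, the tables are descriptive, every value is listed, and adverse events, exposure and rating scales are not assigned by these windows. That is correct and limits the severity.

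**Conclusion.** The concern holds. The mismatch between a week-48 Month 12 target and a 1-year/52-week study is certain from the text, as is the unreconciled conflict between Sections 6.1 and 6.4. The mislabelling is conditional on visit spacing. It is systematic on the stated schedule and on calendar months, mostly present at 30 days, and absent at 28.

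On the stated schedule, the by-visit Month 12 vital-sign summaries would be Month 11 data whenever both visits occurred. True Month 12 values would remain only in listings and in any overall outlier counts. No hypothesis test is affected. This should be fixed before the by-visit safety tables are relied on. Because the windows were added after lock, the visit dates needed to check them were already available.

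**What to change.** 1. State in Sections 6.1 and 6.4 which rule governs each data type. The simpler choice is the nominal visit for all scheduled assessments, as 6.1 already says, with windows used only to place early-termination data.
2. Before rerunning anything, cross-tabulate nominal against windowed visit from the locked data and report how many records change label. If none do, that result closes the labelling question.
3. If windows are kept and the 52-week schedule is confirmed, set targets at 1 + (364/12)k: 31, 62, 92, 122, 153, 183, 213, 244, 274, 304, 335, 365, with midpoint cut-offs. For laboratory, ECG and physical-examination data, use only the scheduled months (1, 3, 6, 9, 12). The midpoints are 61.7, 137.5, 228.5 and 319.5, giving windows 2–61, 62–137, 138–228, 229–319 and 320 onward.
4. Reconcile the stated treatment length (1 year/52 weeks) with the week-48 target, and state the planned visit interval in days. Which length applies is for the sponsor to confirm.

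The cost is SAP wording, one cross-tabulation and, if labels change, a rerun of the by-visit safety tables. No new data are needed.
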